9.4.3 ANALYSIS OF THE SECONDARY ENDPOINT(S)

Secondary Outcomes of Effectiveness Trial - The secondary outcomes are perceived access, quality of life and risk factors for premature mortality. **Access:** Perceived access to OUD services will be measured using a modified version of the 9-item SPIRIT Perceived Access Scale developed for our PCORI trial. The scale is based on theory,¹¹ has excellent internal consistency (κ - 0.89), and concurrent validity with number of mental health encounters ($p=0.016$). **PTSD symptoms** will be assessed using the PCL-5.⁶⁹ **Depression symptoms** will be assessed using the SCL-20.⁷⁰ **Anxiety** will be measured using the Neuro-QOL Measure - *Emotional Distress, Anxiety, Short Form 7a*.^{71,72} **Health Related Quality of Life** will be measured using the Veterans Short Form-12.⁷³ **Risk factors for premature mortality:** Risks, including suicidal ideation (two items from SCL-20), discontinuing MOUD⁶, overdose, suicide attempts, emergency department admission, hospitalization⁷⁴ and death, will be collected from participating clinics as part of the adverse event reporting process. Depending on their observed frequency, these risk factors will be analyzed separately or grouped.

Clinical Mechanism of Action (MOUD Persistence) - Patient self-report will be used to determine whether the patient engaged in MOUD, defined as the ratio of the number of days they reported taking the MOUD medication (numerator) to the number of days during the 6-month follow-up period for which it was prescribed (denominator).⁵¹

Intent to Treat Analysis of Secondary Outcomes and Clinical Mechanism of Action of Effectiveness Trial - Measurement occasions (level 1) will be nested within individuals (level 2) and nested within clinics (level 3). All outcomes will be analyzed with a multilevel model accounting for clustering of observations (level 1) within patients (level 2) and clinics (level 3). Regression models will be specified with the appropriate distribution and link functions to match the dependent variable (linear for the continuous scores, logistic for MOUD engagement and presence of risk factors). The model includes a random intercept and random linear slope to account for person-level clustering and estimate variable time trends across participants. To allow for curvilinear change over time, time will be entered as a nominal variable by including dummy codes for the 3- and 6-month time points. The explanatory variable of interest will be group randomization status (e.g., intervention versus control). Main effects and interaction terms capture the difference between intervention and control group at each wave. Covariates will be included if they are theoretically related to both the dependent variable and the probability of having missing data. An alpha level of 0.05 and two-tailed tests will be used to determine statistical significance. Results for continuous variables will be presented as adjusted differences between groups with confidence intervals. Results for dichotomous variables will be presented as

adjusted odds ratios with confidence intervals. **Missing Data** - We will examine patterns of missing data to determine the degree to which the missing at random assumption (the degree to which missingness is related to variables included in the model) is plausible. With high missing rates, we may use missing data methods to account for missing not at random mechanisms. If warranted, multiple imputation or similar methods will be used to account for missing data on completed or partially completed baseline and follow-up surveys (e.g., skipped items).

Pre-Post Screening Analysis of Pre-Post Trial – Because the clinics will not have the capacity to analyze data at the level of the individual patient, each clinic will calculate the proportion of patients in the pre-screening sample with a new OUD diagnosis and the proportion of patients in the post-screening sample with a new OUD diagnosis. Each clinic will report these two proportions to the investigative team, and we will compile a dataset with 24 observations (2 observations from each of the 12 clinics in each trial) and two variables: 1) proportion with a new OUD diagnosis and 2) a dummy variable indicating pre- or post-screening time period). For each clinic we will compute the change in proportion from pre- to post-screening. Because the pre-screening proportions are expected to be low (~1%)⁷⁵, the change measures will likely be skewed due to a floor effect. Also, the homogeneity of variance assumption could be compromised if the numbers of patients in the denominators vary considerably. For these reasons, we plan to use the non-parametric sign test to evaluate the statistical evidence indicating whether the proportions have changed. The numbers and proportion of the 12 clinics in each trial that see an increase in proportion of documented OUDs will be tabulated. The overall increase in proportion will be estimated with the mean of the clinic changes, weighted by the inverse variances, assuming binomial distributions for the pre- and post-screening numbers of documented OUDs. A bootstrap empirical 95% confidence interval will be computed for the estimate of overall proportion increase.

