9.2 SAMPLE SIZE DETERMINATION

Power Analysis For Pre-Post Trial – Under the assumption of 24 clinics, at least 500 eligible MHS patients in each clinic in each six-month period, a rate of documented OUD of 1% pre-screening, a conservative estimate of 0 correlation between pre- and post-percentages, and an alpha significance level of 0.05, we will have 80% power to detect an increase from a pre-screening percentage of 1% to a post-period percentage of 1.7%.

Power Analysis For Effectiveness Trial - Assuming a coefficient of variation of 0.33 for the continuous outcome of days of illicit opioid use⁶⁷⁶ and SF12V MCS scores⁶⁶⁸⁷, a highly conservative intraclass correlation within clinics of 0.03, 12 clinics per group and 40 patients per clinic (n=960, accounting for NIH Behavioral and Social Intervention Clinical Trial Protocol Template v3.0 - 20180827

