*The table below is intended to capture changes of IRB-approved versions of the protocol, including a description of the change and rationale. A **Summary of Changes** table for the current amendment is located in the **Protocol Title Page**.*

Version	Date	Description of Change	Brief Rationale
2	3.27.2020	
 1. Changed the name of the intervention group from “CHAMP” to “intervention group” and the control group from “CoCM for MHD” to “control group”. 2. Change the trial design from two parallel trials to one trial with two cohorts. 3. Excluded children under the age of 18. 4. Dropped the requirement to recruit clinics from areas with high levels of opioid overdoses. 5. Revised the specifications of the numerator and denominator groups for Aim 1. 6. Added inclusion criteria that patients could be referred into the study. 7. Added inclusion criteria that study participants must have at least two symptoms of opioid use disorder as assessed by a clinician using the DSM-5 checklist. 8. Added that we will be collecting information from the state Prescription Drug Monitoring Program. 9. Added information about the anticipated risks. 10. Revised the consent form to reflect these modifications. 11. Revised the HIPPA authorization form. 	
 1. This was done to increase clarity and to not conflate the study name with the name of the intervention group. 2. This was done to improve the balance of the intervention and control groups. 3. The clinics prefer that we know enroll children in the trial. 4. We needed to relax this requirement in order to recruit enough clinics. 5. These changes were made to accommodate limitations of EHR queries and to increase clarity. 6. This change was made at the request of the participating clinics. 7. This was added to ensure that referred patients meet criteria for opioid use disorder. 8. This information about dispensing was added to triangulate information about prescriptions and patient self-reported use of prescribed opioids. 9. This was added so that we could classify adverse events as anticipated or unanticipated. 10. These revisions were made to ensure that the consent form was consistent with changes to the protocol. 11. The HIPPA authorization form was revised to be compliant with Washington state law.

Version	Date	Description of Change	Brief Rationale

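### The pre-post screening analysis is described for 12 clinics per trial, but its 80% power rests on 24 clinics and the study now lists 42; the counts and the tie rule need to be settled

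*Protocol*

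**What the plan says.** The secondary objective asks whether adding OUD screening raises the proportion of patients with a new OUD diagnosis. Protocol 4.1 describes a single Pre-Post trial, comparing the first six months of the trial with the six months before.

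Protocol 9.2 sets the power, starting from "Under the assumption of 24 clinics, at least 500 eligible MHS patients in each clinic in each six-month period". Its other inputs are that 1% of patients have OUD recorded before screening starts, that the two periods are uncorrelated, and that the level is 0.05. From these it derives 80% power for a rise to 1.7%. It names no test.

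Protocol 9.4.3 describes the analysis. Each clinic reports two proportions, compiled as "24 observations (2 observations from each of the 12 clinics in each trial". For the test, "we plan to use the non-parametric sign test to evaluate the statistical evidence indicating whether the proportions have changed". The number of clinics that rise is then tabulated, again on the basis of 12 clinics per trial. The same section adds an inverse-variance-weighted mean change with a bootstrap interval. It gives no rule for ties.

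Protocol 1.1 and 5.4 list 42 clinics, and 5.4 has all of them introducing universal OUD screening. SAP section 2 explains the total as 24 initial clinics plus 18 added later. The SAP does not cover the screening comparison, so 9.4.3 is the governing text.

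**The concern.** The clinic counts do not agree. Two observations from each of 24 clinics make 48 rows, not 24, and 24 rows make 12 pairs. There is no second trial for another 12 clinics to belong to. The amendment history offers a likely explanation. Its version 2 entry reads "Change the trial design from two parallel trials to one trial with two cohorts", so 9.4.3 probably still carries wording from a two-trial design. The disagreement itself is between 9.4.3, 9.2, 4.1 and 5.4, all of which are current text.

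This is the only test planned for the secondary objective. An analyst following 9.4.3 literally could run two 12-clinic tests with no rule for combining them, or could settle the number of clinics and the treatment of ties after seeing the data. A sign test on 12 clinics is a much weaker instrument than one on 24, so the power in 9.2 would not describe the analysis performed.

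**Working it through.** **Inputs.** From Protocol 9.2: 24 clinics, "at least 500 eligible MHS patients in each clinic in each six-month period" (500 used), 1% before, 1.7% after, zero correlation between periods, level 0.05. From 9.4.1: two-tailed tests. From 9.4.3: sign test on clinic-level changes, and 12 clinics in the dataset as described.

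**Step 1: one clinic.** Let X ~ Bin(500, 0.01) before and Y ~ Bin(500, 0.017) after, independent.

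- P(rise) = Σ P(Y = k) · P(X < k) = 0.796
- P(tie) = Σ P(X = k) · P(Y = k) = 0.070
- P(fall) = 1 − 0.796 − 0.070 = 0.134

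**Step 2: critical values.** Take the smallest r with 2 · P(Bin(N, 0.5) ≥ r) ≤ 0.05.

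- N = 24: r = 18 (p = 0.023; 17 rises give 0.064)
- N = 12: r = 10 (p = 0.039; 9 rises give 0.146)

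**Step 3: reproduce the plan's figure.** With ties counted as non-rises, power = P(Bin(24, 0.796) ≥ 18) = 79.6%, which matches the stated 80%. Alternatives tried at 24 clinics do not match:

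- two-sided sign test with ties dropped: 93.9%
- two-sided sign test with ties split at random: 90.3%
- one-sided sign test with ties as non-rises: 90.2%
- paired t: 99.4%
- pooled two-proportion z: 99.7%

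The power statement therefore appears to describe a two-sided exact sign test on 24 pairs with ties as non-rises.

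**Step 4: the same test on 12 clinics.** Power = P(Bin(12, 0.796) ≥ 10) = 0.280 + 0.199 + 0.065 = 54.4%. With ties dropped, the result is averaged over the random number of untied clinics, each rising with probability 0.796 / (1 − 0.070) = 0.856.

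| Clinics | Rises needed (no ties) | Power, ties as non-rises | Power, ties dropped |
|---|---|---|---|
| 12 | 10 | 54.4% | 62.7% |
| 24 | 18 | 79.6% | 93.9% |
| 42 | 28 | 98.4% | 99.8% |

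The tie rule alone moves power by 62.7 − 54.4 = 8 points at 12 clinics and by 93.9 − 79.6 = 14 points at 24.

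**Step 5: sensitivity to the inputs.**

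- *Clinic size.* Sizes above the minimum are my assumption. The 12-clinic test has 76–81% power at 750 patients per clinic per period and 88–91% at 1,000.
- *Between-clinic spread.* The figures above allow binomial variation only. Assume an independent between-clinic SD of 0.2 to 0.4 percentage points in each period (not in the documents). Simulated power on 24 clinics then falls to about 73–60% (ties as non-rises) or 90–81% (ties dropped), and on 12 clinics to about 50–41% or 58–46%.

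**Step 6: would a different test be better?** A Wilcoxon signed-rank test has about 99% simulated power on 24 clinics and 84–85% on 12. I also simulated its error rate when the median change is zero but clinics drift differently, assuming a median baseline of 1%, log-SD of baseline rates 0.5, and 500 per clinic. On 24 clinics it rejects about 5% of the time at a log-change SD of 0.3, 7% at 0.5 and 11% at 0.8. The sign test stays near 3% throughout.

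**The case against.** **The 12 may never reach the test.** The sentence specifying the sign test gives no clinic count, and nothing states that two tests will be run. The 12 appears in the dataset description and the tabulation, and is probably leftover text. This stands. A reader might infer that the planned test is known to have only 54% power, but the documents support only the conditional: that is its power if run on 12 clinics.

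**The low figures are computed at the minimum clinic size.** Protocol 9.2 gives 500 as a lower limit, and larger clinics raise the power. This also stands, although between-clinic spread, which 9.2 leaves out, pulls the other way.

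**With 42 clinics there may be no shortfall.** If every clinic supplies both periods, the sign test has 98–99.8% power at the planning values. The documents do not say whether the 18 added clinics contribute pre-post data, so this cannot be assumed, but neither can 24.

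**A tempting stronger reading is that the sign test is the wrong choice** and that a signed-rank test should replace it to reach 99%. The documents do not support that. The comparison of 54% with 99% mixes two changes, and using 24 clinics alone restores 80–94%. Protocol 9.4.3 chooses the sign test because it expects skewed changes. Under a strict null of equal rates in every clinic, skew is not a problem for the signed-rank test. When clinics drift unequally from a base near 1%, it can over-reject, so the protocol's caution is reasonable. Nor is the size of the changes ignored, since the weighted mean change and its bootstrap interval use it.

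**Conclusion.** The inconsistency is real, and the point should be corrected. The dataset and tabulation in 9.4.3 fit neither the single Pre-Post trial in 4.1, nor the 24 clinics in 9.2, nor the 42 clinics now in the study. The choice of test is sound. The number of clinics and the tie rule are what is unsettled.

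The cost of following the 12-clinic wording would be a drop from about 80% to 54% power with ties as non-rises, or from 94% to 63% with ties dropped. These figures rest on exactly 500 patients per clinic per period, the planning rates, independence between periods and no between-clinic spread.

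**What to change.** In Protocol 9.4.3, replace the 12-clinics-per-trial wording, in both the dataset description and the tabulation, with one sign test across all clinics that supply pre and post data. State that number after reconciling 12, 24 and 42, with two observations per clinic (48 rows for 24 clinics, 84 for 42). State how ties are handled.

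In 9.2, name the test and restate the power for that number of clinics and that tie rule. If separate 12-clinic tests are intended, say so, say how they are combined, and give their power as about 54–63% at 500 patients per clinic.

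A signed-rank test can be listed as an optional sensitivity analysis, with a note that it can over-reject when clinic changes are heterogeneous and skewed.

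The cost is a few sentences, a check of which clinics contribute pre-post data, and no new data collection. Because the pre and post periods have probably ended for the initial clinics, the count and tie rule should be fixed and dated before the clinic proportions are compared.

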10.1.8 DATA HANDLING AND RECORD KEEPING

10.1.8.1 DATA COLLECTION AND MANAGEMENT RESPONSIBILITIES

Sources of Materials

Sources of research materials include the following:

EHR Data (Non-Indefinable) – Pre- and Post-Screening data (numerator [OUD diagnosis] and denominator [unique patients] will be calculated by each healthcare organization using EHR queries and recorded in an excel spreadsheet. The excel spreadsheet (which contains no patient health or identifying information), will be emailed to the study team at the University of Washington. Data will be reviewed by University of Washington statisticians and data managers and discussed with the on-site study team. This data will be used for the Secondary Objective (Pre-Post Trial).

Eligibility Data and Consent Forms – The eligibility information for all patients screening positive for OUD will be entered directly into RedCap by the on-site study team. Signed consents forms, will be scanned and attached to the RedCap study portal. Eligibility data will be reviewed by a University of Washington PI and the study coordinators, and discussed with the on-site study teams. This data will be used for the Primary Objective (Effectiveness trial).

Personal Identifying Information – Identifying information (e.g., name, address, telephone number, email, and contacts) about patients consenting to be in the Effectiveness trial will be stored in a single file along with a unique study identifier. This data will be used for the Primary Objective (Effectiveness trial).

Surveys - The patient web/telephone survey will be administered at baseline, 3- and 6-month follow-ups. All survey responses are stored directly into a RedCap database. This data will be used for the Primary Objective (Effectiveness trial).

Adverse Events – Information about all Adverse Events, Serious Adverse Events, Unanticipated Problems, and Potential Loss of Confidentiality will be entered directly into RedCap by the on-site study team and reviewed/edited by the research team. This data will be used for the Primary Objective (Effectiveness trial), as well as for regulatory purposes.

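### Inverse-variance weights built from each clinic's own near-1% proportions bias the estimated rise in OUD detection downwards at the planning values (0.65 instead of 0.70 points); size weights remove this at little cost

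*Protocol*

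**What the plan says.** Protocol 9.4.3 (Pre-Post Screening Analysis) has each clinic report its proportion of patients with a new OUD diagnosis before and after screening began. The evidence for a change comes from a sign test on the clinic-level changes. The size of the change is a separate estimate: "The overall increase in proportion will be estimated with the mean of the clinic changes, weighted by the inverse variances", assuming binomial counts in both periods, with a bootstrap 95% confidence interval. The section does not say whether the variance uses each clinic's own proportions or rates pooled over clinics. It also does not name the bootstrap unit or give a rule for zero counts.

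The same section expects pre-screening rates of about 1% and warns that "the homogeneity of variance assumption could be compromised if the numbers of patients in the denominators vary considerably". Yet the dataset it describes holds "two variables: 1) proportion with a new OUD diagnosis and 2) a dummy variable indicating pre- or post-screening time period", with no denominators. Protocol 10.1.8.1 shows that each organization does supply a numerator and a denominator.

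The planning values are in Protocol 9.2: "Under the assumption of 24 clinics, at least 500 eligible MHS patients in each clinic in each six-month period". The rate before screening is taken as 1%, and the stated power is 80% for a rise to 1.7%. The SAP does not cover the pre-post trial, so nothing later settles the weights.

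**The concern.** At rates near 1% the binomial variance p(1 − p)/n is almost proportional to the observed count. Of two clinics of equal size, the one that happened to record fewer diagnoses gets the larger weight. A low post-period count both lowers the clinic's change and raises its weight, so the weighted mean is pulled below the true rise. Adding clinics does not help, because the bias arises within each clinic.

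If true rates also differ between clinics, the weights follow the rates as well as the sizes, and the result is neither the average increase among patients nor the plain average over clinics.

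This weighted mean and its interval are the only planned measure of how much screening raised detection, which is the secondary objective. At stake is the reported size of the gain, not whether a gain is declared.

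**Working it through.** **Inputs.** Protocol 9.2: 24 clinics, n = 500 per clinic per period (a minimum), p1 = 1.0%, p2 = 1.7%, pre/post correlation 0, alpha 0.05. Protocol 9.4.1: two-sided tests. True rise: 1.7 − 1.0 = 0.70 points.

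**The plan's own figure.** With independent Binomial(500, 1%) and Binomial(500, 1.7%) counts, a clinic shows an increase with probability 0.796, a tie with 0.070 and a decrease with 0.134. The exact two-sided sign test on 24 clinics needs 18 increases. With ties counted as non-increases the power is 0.796, which reproduces the stated 80%. The test does not use the weights.

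**The estimator.** With clinic proportions a (pre) and b (post), change d = b − a:

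w = 1 / [a(1 − a)/n + b(1 − b)/n], estimate = Σwd / Σw.

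**Two clinics of 500 patients per period, by hand.**
- 4 to 6 cases: a = 0.008, b = 0.012. Variance = (0.007936 + 0.011856)/500 = 0.000039584; w = 25,263; d = 0.4 points.
- 6 to 11 cases: a = 0.012, b = 0.022. Variance = (0.011856 + 0.021516)/500 = 0.000066744; w = 14,983; d = 1.0 point.

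The plain mean is (0.4 + 1.0)/2 = 0.70. The weighted mean is (25,263 × 0.4 + 14,983 × 1.0)/(25,263 + 14,983) = 25,088/40,246 = 0.62.

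**Simulation at the planning values** (equal true rates, at least 40,000 data sets per setting; results in percentage points):

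| Weights | Mean | SD | RMSE |
|---|---|---|---|
| Inverse variance, clinic's own proportions | 0.650 | 0.145 | 0.153 |
| Size (Mantel-Haenszel) | 0.701 | 0.149 | 0.149 |
| Inverse variance, rates pooled over clinics | 0.701 | 0.149 | – |

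The bias is 0.650 − 0.700 = −0.050 (−7%), or 0.050/0.145 = 0.34 of a standard error. The third of clinics with the fewest diagnoses carries 44% of the weight with 33% of the patients. With a percentile bootstrap that resamples clinics, 95% interval coverage is 92.4% with own-proportion weights and 93.3% with size weights (2,000 data sets).

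**Number of clinics and continuity corrections (own-proportion weights).** The mean is 0.651 to 0.654 with 12 clinics and 0.649 with 42. Adding 0.5 to zero counts gives 0.648, and adding 0.5 to all cells gives 0.654. With no true change the bias is zero.

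**Clinic size, equal rates (own-proportion weights).** 0.675 (−4%) at 1,000 per period; 0.688 (−2%) at 2,000; 0.686 (−2%) with denominators spread over 500 to 4,000 (assumed spread).

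**True rates differing between clinics.** The documents give no figure for this. I assumed a log-SD of 0.3 to 0.5 and 24 clinics of 500 unless stated:

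| Pattern of rise | Own-proportion mean | Error |
|---|---|---|
| Proportional to baseline | 0.585 to 0.486 | −16% to −31% |
| Equal absolute rise | 0.643 to 0.633 | −8% to −10% |
| All clinics reach 1.7% | 0.675 to 0.720 | −4% to +3% |
| Proportional, n = 2,000, log-SD 0.5 | 0.538 | −23% |
| Same post rate, n = 2,000, log-SD 0.5 | 0.767 | +10% |
| Proportional, sizes 500 to 2,500, log-SD 0.5 | 0.533 | −24% |

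Size weights average 0.70 in every row. For the proportional rise at n = 500, coverage with own-proportion weights falls to 87.5% (log-SD 0.3) and 71.2% (log-SD 0.5), against 93.6% and 92.8% with size weights.

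**The case against.** The strongest reply is that this is an ambiguity rather than a wrong analysis. A variance with rates pooled over clinics also fits the wording and removes the bias, so one clause would settle it. That stands as an alternative remedy. It does not make the present text safe: each clinic reports its own two proportions, and an analyst following the section would most naturally plug those in.

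The effect at the documents' own values is also modest. It is a third of a standard error, it understates the benefit, and it cannot create a gain where there is none. The 500 is a floor; at 2,000 per period with equal rates the RMSEs are almost the same (0.0750 against 0.0746). All of this stands. The larger errors rest on an assumed spread of true rates and should not set the seriousness of the point.

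Size weights are not best in every respect. If all clinics reach the same post rate, the planned estimator has the lower RMSE at 500 per period (0.154 against 0.161 at log-SD 0.3; 0.163 against 0.184 at 0.5). Size weights also target the average increase among patients. If clinic size and rate are correlated, that differs from the mean over clinics: with sizes 500 to 4,000, log-SD 0.5, a proportional rise and correlation of −0.5 or +0.5 (all assumed), size weights average 0.61 or 0.80 while the clinic mean is 0.70. The planned weights give 0.47 or 0.61 and so miss both targets. The target therefore needs to be stated, but this does not favour the planned weights.

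Finally, the bootstrap scheme is unspecified, and one version does better: a binomial bootstrap at pooled rates with a basic interval covered 94.2% under equal rates. A basic interval from resampled clinics covered 91.3%. An improved interval would still surround a biased point estimate.

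**Conclusion.** The concern holds, conditional on each clinic's own observed proportions entering the variance. On that reading the headline estimate for the secondary objective averages 0.65 instead of 0.70 points at the planning values, with the bias shrinking to 2% at 2,000 patients per period if true rates are equal. If rates differ between clinics the error can be much larger and can go in either direction, but that rests on an assumed spread. The sign test, its 80% power and the primary objective are untouched. Separately, and on any reading, the planned weights cannot be computed from the two-variable dataset the section describes. The change is worth making because it is cheap and fixes a choice that could otherwise be made after seeing the data.

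**What to change.** In Protocol 9.4.3, or in a SAP section for the pre-post trial:

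- Estimate the overall increase as the Mantel-Haenszel risk difference, Σw(b − a)/Σw with w = n1·n2/(n1 + n2), where n1 and n2 are the clinic's pre and post denominators. State that the target is the average increase among patients.
- Compute the 95% interval from a bootstrap that resamples clinics, and name the interval type.
- Add each clinic's numerators and denominators to the analysis dataset.
- Editorial: refer to all participating clinics instead of 12 clinics in each trial.

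If inverse-variance weighting is kept, state that rates pooled over clinics enter the variance; this removes the bias too.

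The cost is wording only, since the counts are already collected. The statistical price is a slightly larger SD: 0.149 against 0.145 points with equal rates, and 0.166 against 0.147 with a proportional rise at log-SD 0.5. There is also a higher RMSE in the pattern where all clinics reach the same post rate.
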